5.4 Sample size calculation

(ICH E3; 9.7.2. ICH E9; 3.5)

The primary objective is to identify, in human tumor samples, biomarker changes associated with short exposure to AZD2281 as potential predictors of activity in Endometrial Carcinoma (EC). The primary endpoint is the difference between pre and post treatment immunostaining of cyclin D1, Ki67 and active caspase 3 on endometrial tumor tissue, after four weeks of treatment. Therefore, the primary analysis will be based on comparing pre and post treatment immunostaining on target biomarkers. The histological

score will be obtained by applying the following formula: $Hscore = 1x(\%light staining) + 2x(\%moderate staining) + 3x(\%strong staining)$. Although a preliminary power analysis has been performed, in agreement with the exploratory nature of phase 0 studies, the sample size has been limited to 36 patients (It is expected that each participating site includes an average of about 6-10 patients) for clinical and practical considerations, rather than statistical ones (Kummar et al 2009).

Analysis will be performed in accordance with a statistical evaluation scheme specifically developed for Phase 0 trials (Rubinstein et al 2010). In the analysis we will define response at the patient level (patients with significant inhibition of biomarkers), before analyzing the number of responding patients in the study sample.

Definition of response at the patient level:

Significant inhibition of biomarker activity is defined as the reduction in biomarker levels after four weeks treatment exposure (compared to baseline) that should satisfy two criteria: reduction is at least 50 % (biological), and reduction is sufficient when compared to the variation among the baseline values, to yield 95 % statistical confidence that it is not due to chance variations.

Variability will be measured on log-transformed values. The standard deviation (SD) will be the square root of baseline inter-patient variance. Pre- and post-treatment difference of log PIK1 values will be compared to the threshold of 1.6448 SD (normal distribution is used because number of samples is higher than 30), to establish statistically significant reduction at the one-sided 0.05 level.

Definition of a significant effect at study sample:

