Significant inhibition of biomarker activity will be declared if 5 of 36 patients have significant inhibition at patient level. Based on these assumptions, there is a 95% power to detect a true 35% rate of significant inhibition with an overall alpha error below 10%. As we consider three biomarkers in the primary analysis (cyclin D1, Ki67 and active caspase 3), the type I error was divided into 3,3% (<5%) for each analysis. Power and type I error has been derived from the binomial distribution (Rubinstein et al 2010), according to (A'Hern 2001).

Study dropouts

We assume the loss of patients between recruitment and end of study. Study dropouts will be analyzed as patients not displaying significant inhibition of the biomarker activity.

5.5 Randomization and blinding.

(ICH E3; 9.4.3, 9.4.6. ICH E9; 2.3.1, 2.3.2)

The randomization or blinding was not planned in this study.

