6 ANALYSIS SEQUENCE

6.1 Interim analysis

Prior to the completion of the study, an interim analysis with a cut-off dated 08-May-2018 will be performed in case the study was not completed up to that date. The results will be presented at the ASCO annual meeting 2018. The results will include patient characteristics in the different analysis populations. Primary and secondary biomarker analyses of the samples available up to that date and safety analyses.

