7.2 Populations for analysis

(ICH E3; 9.7.1, 11.4.2.5. ICH E9; 5.2)

Full analysis set

This set will include all the patients who have received the treatment. This set will also be the safety analysis set.

Per protocol set

This set will include all the patients of the full analysis set that do not have major protocol violations that may affect the assessment of treatment in the primary variable (e.g., non-evaluable patients for

biomarkers). The definition of these deviations is described in section 9.1. For the analysis of secondary variables, the number of evaluable patients for a certain biomarker analysis set will be considered.

Sensitivity analysis

The primary biomarker analysis (significant inhibition of cyclin D1, Ki67 and active caspase-3) and the secondary analyses will be performed in the full analysis set and the per protocol population.

The safety analyses will be performed in the full analysis set.

PKD population

We propose to analyze and model pharmacokinetics (PK), pharmacokinetics-pharmacodynamic (PBMC) and AZD2281 concentration, considering all patients with a complete treatment concentration-time profile.

Analyses will not be repeated between different analysis populations if they only differ by 10% patients. The largest analysis population will be used for the analyses.

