7.6 Missing data imputation

(ICH E3; 9.7.1, 11.4.2.2. ICH E9; 5.3. EMA Guideline on Missing Data in Confirmatory Clinical Trials)

Patients without quantitative biomarker values at the baseline visit will be assigned the mean of the patients at that visit. Patients without quantitative values at the follow-up visits will be assigned the same value as in the baseline visit. This imputation is intended to be conservative and go against the study objective (to detect a significant evolution between pre- and post-treatment biomarker values). In the case of qualitative variables, the lack of mutation or the characteristic analyzed will be assumed.

The different study populations where the different analyses will be performed will help to assess the imputation on the results. The analyses are only considered positive if the result is equivalent in all the analysis populations used.

7.7 Analysis of the specific effects of each site.

(ICH E3; 9.7.1, 11.4.2.4. ICH E9; 3.2)

The number of patients enrolled in each site will be described. Considering the small sample size, no analyses are expected to adjust the results by the site effect.

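### The 95% per-patient confidence and the 3.3%/<10% type I error rest on a pre/post correlation and a log-SD that the plan never states

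*SAP*

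**What the plan says.** SAP 5.4 calls a patient a responder on a biomarker if the level falls by at least 50% and the fall is large enough "to yield 95 % statistical confidence that it is not due to chance variations". The second criterion is made operational on the log scale: "The standard deviation (SD) will be the square root of baseline inter-patient variance". Then: "Pre- and post-treatment difference of log PIK1 values will be compared to the threshold of 1.6448 SD", which the section describes as one-sided significance at 0.05.

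At study level, 5 responders among 36 patients are enough to declare inhibition. The section gives 3.3% type I error for each of three biomarkers and less than 10% overall, and explains that "Power and type I error has been derived from the binomial distribution". SAP 7.8 repeats both figures. It also requires p-values below 3.3% at interim and final analysis and in both analysis populations.

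Four other provisions affect the error rate:
- SAP 5.4: "Study dropouts will be analyzed as patients not displaying significant inhibition of the biomarker activity".
- SAP 6.1: the interim takes place only "in case the study was not completed up to that date".
- SAP 7.2: "Analyses will not be repeated between different analysis populations if they only differ by 10% patients"; the larger population is then used.
- SAP 7.6: "Patients without quantitative biomarker values at the baseline visit will be assigned the mean of the patients at that visit".

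Neither document gives a pre/post correlation, a within-patient or test-retest variance, or a value for the log-SD.

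**The concern.** The quantity tested is a change within one patient, but the yardstick is the spread between patients at baseline. These are different standard deviations, and they coincide only for one value of the pre/post correlation. If the two samples from a patient agree less closely than that, patients on an inactive drug cross the threshold more often than 5% of the time, and five chance responders out of 36 are easier to reach. If they agree more closely, the rule is stricter than stated.

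This rule produces the primary result, and SAP 3.1 says phase 0 studies serve go/no-go decisions. A reader of the result would take the 3.3% and <10% as properties of the design, although they depend on two unstated quantities.

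There is also a drafting slip: the rule is written for log PIK1, which is not one of the three primary biomarkers (cyclin D1, Ki67, active caspase 3).

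**Working it through.** **Inputs from SAP 5.4.** n = 36; at least 5 responders; per-patient one-sided rate 0.05; threshold 1.6448 × SD; 50% reduction, which is ln 2 = 0.693 on the natural-log scale; three biomarkers. **Assumed:** normal log H-scores, equal pre and post variances, no drug effect. Rho and the log-SD s are shown over a range because the documents support no value.

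**Step 1: the plan's own figure.** P(Bin(36, 0.05) ≥ 5) = 3.24%. Three biomarkers give 3 × 3.24% = 9.7% by summation, or 1 − (1 − 0.0324)^3 = 9.4% if independent. So 3.3% and <10% reproduce, provided the per-patient rate is 5%. (This covers alpha only. The 95% power stated for a true 35% rate does not reproduce: the exact value is 99.9%. That is a separate matter.)

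**Step 2: the per-patient rate.** The SD of the change is s·sqrt(2(1−rho)), so the false-response rate is

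f = Φ(−max(0.693, 1.6448·s) / (s·sqrt(2(1−rho)))), and alpha = P(Bin(36, f) ≥ 5).

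The 50% criterion is slack when s > 0.693/1.6448 = 0.42. Then s cancels, and f = 5% only when 2(1−rho) = 1, that is rho = 0.5.

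**Step 3: alpha per biomarker, 50% criterion slack.** The last four columns are simulations at s = 0.6 with the SD estimated from the 36 baselines. Dropouts means 30 of 36 evaluable (assumed). Interim means an assumed interim n of 20, 24 or 28, needing 4, 4 or 5 responders. Those are the smallest counts with p < 3.3% at a 5% rate: 1.6%, 3.0% and 1.2%, whereas 4 of 28 gives 4.9%.

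| rho | f | One look, SD known | One look, SD estimated | Dropouts only | Interim + final only | Both |
|---|---|---|---|---|---|---|
| 0 | 12.2% | 45.5% | 47% | 32% | 21–31% | 13–19% |
| 0.3 | 8.2% | 17.1% | 20% | 12% | 7–11% | 4–6% |
| 0.4 | 6.7% | 8.9% | 12% | 6.7% | 4–6% | 2.0–3.3% |
| 0.5 | 5.0% | 3.24% | 5.5% | 2.9% | 1.8–2.8% | 0.9–1.5% |
| 0.6 | 3.3% | 0.6% | 1.8% | 0.9% | 0.5–0.8% | below 0.5% |

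Estimating the SD is enough to lift one-look alpha above 3.3% at rho = 0.5. With the SD estimated, 3.3% is reached at rho of about 0.55.

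**Step 4: small log-SD, where the 50% criterion binds (SD known).**

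| s | rho 0 | rho 0.3 |
|---|---|---|
| 0.30 | 3.5% | 0.2% |
| 0.35 | 16.1% | 2.6% |
| 0.40 | 36.4% | 11.2% |

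Alpha equals 3.33% at s of about 0.30, 0.36 and 0.39 for rho 0, 0.3 and 0.4. Below about 0.30 it stays at or near 3.3% for any rho of 0 or more.

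**Step 5: mean imputation (SAP 7.6).** Section 5.4 does not say whether the SD is taken before or after missing baselines are replaced by the mean. If after, the SD and hence the threshold shrink. At rho 0.5, s = 0.6, one look:

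| Baselines missing (assumed) | SD ratio | Full-set alpha, imputed SD | Full-set alpha, observed SD |
|---|---|---|---|
| 3 of 36 | 0.956 | about 9% | about 6% |
| 4 of 36 | 0.941 | about 10% | about 6% |

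Three of 36 is 8.3%, under the 10% limit in SAP 7.2, so only the larger set would be analysed. With 4 of 36, if those patients leave the per-protocol set, requiring both populations lowers alpha to about 3.9%. If they stay, the two sets coincide and nothing is gained.

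**The case against.** The strongest reply is that no error in a known direction has been shown. That stands. A reader might infer from the upper rows of the table that the design is anti-conservative, but nothing in the documents supports a low rho. Rho = 0 would mean that two samples from one patient's tumour resemble each other no more than samples from two patients, which is an extreme. With rho above about 0.55, or a log-SD below about 0.30, alpha is at, near or below the stated level.

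A second reply is that the plan's own safeguards lower alpha, and this stands in part. A reader might infer that they cannot help once rho is below 0.5. That is too broad: with dropouts and an interim together, rho of 0.4 is brought to about 3.3% or less. They leave 4–6% at rho 0.3 and 13–19% at rho 0. With only one of the two, rho of 0.4 remains above 3.3%. SAP 6.1 makes the interim conditional, and no dropout rate is given.

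Third, missing baselines should be uncommon, because eligibility requires a centrally checked biopsy, repeated if inadequate. That is fair, and the counts of 3 and 4 are assumptions. A reader might also infer that imputed patients always remain per-protocol, so that the two-population rule gives no relief. The SAP does not settle this. The section 8 row for an uncollected pre-treatment biopsy keeps them in, the row for missing or non-evaluable values leaves it case by case, and section 7.2 names biomarker non-evaluability as an example of exclusion.

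Fourth, a paired Wilcoxon comparison is already planned (SAP 7.1; Figure 2 in 9.1) and needs neither rho nor the between-patient SD. It limits the harm but does not repair the responder error rate.

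Finally, the SAP attributes its scheme to a cited phase 0 method and says the sample size was set on practical grounds. That explains the choice of rule; it does not supply the two missing quantities.

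**Conclusion.** The point holds as a missing assumption behind stated error rates, and should be fixed. The binomial step for alpha is right, but its 5% input is secured only at rho = 0.5 when the log-SD exceeds about 0.42. Across rho 0.3 to 0.6, one-look alpha per biomarker runs from 17.1% to 0.6% with the SD known, and from about 20% to 1.8% with it estimated, against 3.3% stated. The dropout and interim rules combined cut this to about 4–6% at rho 0.3 and to 3.3% or less from rho 0.4 upward, if both come into play. Imputing baselines before computing the SD would add roughly 3 to 4 percentage points in the full set under the assumptions shown.

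These figures rest on normal log H-scores, equal pre and post variances, and the assumed evaluable, interim and missing counts. They do not show that the trial's actual type I error is above 3.3%; the documents leave that open in both directions. For an exploratory study the need is an honest statement of the error rate, not a new design.

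**What to change.** - In SAP 5.4 and 7.8, stop presenting 95% confidence and 3.3%/<10% as achieved. State the rho and log-SD under which they hold.
- Tabulate alpha over a range of both (for example rho 0 to 0.8, log-SD 0.3 to 0.8), for one look and under the dropout and interim-plus-final rules combined.
- State that the baseline SD is computed from observed baselines, not mean-imputed ones, and reconcile SAP 7.2 with the section 8 rows on missing baselines.
- Report the observed baseline log-SD and pre/post correlation for each biomarker beside the responder count and the planned Wilcoxon result. The correlation in treated patients is only a guide, because spread in drug response lowers it.
- Replace log PIK1 with the log H-score of each primary biomarker.

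Keep the primary threshold and the 50% criterion. An extra responder count at 1.690·sqrt(2) times the baseline SD (about 3% alpha at rho 0, less above it) is optional. It is calibrated to a correlation that nothing in the documents supports, and it has lower power.

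The cost is SAP wording and one table, with no new data. The downside is that the stated error rate becomes less favourable.

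### The 3.3% error per marker for the 5-of-36 rule treats an SD estimated from the trial's own baselines as known; it is not assured, and the stated 95% power is not the power of this rule

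*SAP*

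**What the plan says.** SAP 5.4 sets a two-level rule for each of cyclin D1, Ki67 and active caspase 3.

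- **Patient level.** The reduction must be at least 50% and must also exceed chance variation. On the yardstick: "Variability will be measured on log-transformed values", and "The standard deviation (SD) will be the square root of baseline inter-patient variance". The pre/post difference is set against a cut-off of 1.6448 SD, with the reason given in brackets ("normal distribution is used because number of samples is higher than 30"), in order "to establish statistically significant reduction at the one-sided 0.05 level".
- **Study level.** "Significant inhibition of biomarker activity will be declared if 5 of 36 patients have significant inhibition at patient level".
- **Operating characteristics.** The SAP claims that "there is a 95% power to detect a true 35% rate of significant inhibition with an overall alpha error below 10" per cent. It allots 3.3% to each of the three markers and says that power and type I error come from the binomial distribution.

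Dropouts count as non-responders (SAP 5.4). SAP 7.6 and 7.8 add that a result is positive only if it agrees across the analysis sets and, if an interim is held, at both interim and final analysis.

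**The concern.** The binomial figure holds if each patient has exactly a 5% chance of a false response, independently of the others. The rule as written strains both conditions.

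- **Rate.** The SD is a sample quantity with 35 degrees of freedom, so a normal quantile gives a false-response rate slightly above 5%.
- **Independence.** All 36 patients are measured against the same estimated SD. When it is low by chance, the bar drops for everyone at once, so the responder count varies more than a binomial count.

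Having more than 30 samples makes the first effect small. It says nothing about the second, which is the larger. At stake are the per-marker and overall error rates of the primary decision rule, in a study that SAP 3.1 describes as informing a go or no-go decision. The power figure beside them also does not match the rule.

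**Working it through.** **Inputs.** From SAP 5.4: n = 36; success at 5 or more responders; per-patient null rate 0.05, one-sided; cut-off 1.6448 SD; SD from baseline log values; at least 50% reduction, i.e. a log fall of at least ln 2 = 0.693; target rate 35%. Assumed, because the documents do not give them: the baseline log SD, the pre/post correlation, normality of log H-scores, and that the SD comes from this trial's own baselines (no other source is named).

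**1. The plan's type I error reproduces.** With X binomial (36, 0.05):

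P(X ≥ 5) = 1 − (0.1578 + 0.2990 + 0.2753 + 0.1642 + 0.0713) = 0.0324.

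Three markers: 3 × 3.24% = 9.7%, below 10%.

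**2. The stated power does not reproduce.** With X binomial (36, 0.35), P(X ≥ 5) = 99.9%. The rule reaches 95% at a true rate of about 24% (94.8% at 0.235, 95.5% at 0.24).

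**3. When the plan's 5% is right.** If baseline and post-treatment SDs are equal, SD(change) = baseline SD × √(2 − 2ρ). The two are equal only at ρ = 0.5, so that value is used to keep the plan's own null.

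**4. Replace the known SD by the estimated one and change nothing else.** Trials of 36 normal log pairs were simulated with no drug effect and ρ = 0.5, taking the SD from the same 36 baselines (1,000,000 trials for the main figure, standard error 0.02 points).

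- Mean per-patient false-response rate: 5.35%.
- Variance of the responder count: about 1.18 times binomial.
- P(5 or more of 36) = 5.63%.
- Three markers: 3 × 5.63% = 16.9% as a sum; 1 − (1 − 0.0563)³ ≈ 16% if independent.

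A plain binomial at 5.35% gives only about 4.1%, so most of the excess over 3.24% comes from the shared threshold. Using the t quantile on 35 degrees of freedom (1.690) instead of 1.6448 leaves about 4.4%.

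**5. Add the 50% criterion (ρ = 0.5, 36 evaluable).** It overtakes 1.6448 SD when the SD is below 0.693 / 1.6448 = 0.42, and it already cuts off low SD estimates somewhat above that.

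| Baseline log SD | P(5 or more of 36) |
|---|---|
| 0.40 | 1.2% |
| 0.45 | 3.2% |
| 0.50 | 4.8% |
| 0.60 or more | 5.5–5.6% |

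**6. Dropouts as non-responders (ρ = 0.5, 50% criterion not binding, SD from evaluable patients).** About 4.8% with 34 evaluable, 4.0% with 32 and 3.3% with 30. Taking the SD from all 36 baselines gives slightly lower values.

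**7. Correlation (log SD 0.7, 36 evaluable).**

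| ρ | SD(change) / baseline SD | 5 of 36 | 6 of 36 |
|---|---|---|---|
| 0.25 | 1.22 | 24% | 12% |
| 0.40 | 1.10 | 12% | 5.0% |
| 0.50 | 1.00 | 5.6% | 2.1% |
| 0.55 | 0.95 | 3.4% | 1.2% |
| 0.60 | 0.89 | 1.8% | 0.6% |

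**8. Power of 6 of 36 at 35%.** Exact binomial: 99.6%.

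**The case against.** The strongest reply is that 5.6% is a scenario and not a property of the trial. It needs a correlation of 0.5, normal logs of a score bounded at 300, a log SD of about 0.6 or more, and no losses. A correlation of 0.55 or a log SD of 0.45 brings the error back to about 3.3%. SAP 5.4 expects losses and counts them against the drug; SAP 7.6 carries the baseline value forward for a missing follow-up, so such a patient cannot respond. The agreement conditions in SAP 7.6 and 7.8 can only lower the error further. The study is exploratory, and its size was set on practical grounds.

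All of this stands, and it limits the claim. A reader might infer that the rule's error is 5.6% per marker, or 17% overall. The documents do not support that, since those figures describe one analysis of 36 complete patients under assumed inputs.

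The reply does not rescue 3.3% as stated. The SAP derives that figure from the binomial alone, gives no SD, correlation or dropout rate, and does not quantify the agreement conditions. The interim is conditional, and SAP 7.2 waives repeat analyses when the sets differ by only 10%. Where a low SD protects the error rate, the protection comes from the 50% criterion and not from the argument the SAP gives.

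**Conclusion.** The point holds in conditional form. The binomial arithmetic for type I error is correct, but its premises are not met when the SD is estimated from the trial's own baselines. Under the conditions that make the plan's 5% exact, a single analysis of 36 evaluable patients has an error of about 5.6% per marker at log SD 0.6 or more (16–17% over three markers), against 3.24%. It falls to 3.2% or less at log SD 0.45 or below, and to about 3.3% with 30 evaluable patients. Without the SD and the correlation, neither 3.3% nor 5.6% can be asserted; the stated figure is not assured.

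The power statement is wrong without any simulation assumption: 99.9% at a 35% rate, not 95%. A reader might take the mismatch as a sign of too little power; the error runs the other way.

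A reader might also infer that moving to 6 of 36 restores error control in general. It does so only if the SD of the change does not materially exceed the baseline SD. Judging a within-patient change by a between-patient SD is a separate and potentially larger problem.

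Severity: should be fixed. The figures support the primary decision rule and are cheap to correct, but the study is exploratory and the excess is conditional.

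**What to change.** In SAP 5.4:

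1. Require 6 of 36 responders per marker. Under the same assumptions this gives about 2.1% or less per marker (3 × 2.1% ≈ 6% overall), with 99.6% power at 35%.
2. State the 5% per-patient null rate and where the SD comes from.
3. Report the simulated type I error with the SD estimated, over a range of log SD, pre/post correlation and number evaluable.
4. Correct the power statement for the rule adopted. If 5 of 36 is kept, it is 99.9% at 35%, with 95% reached at about 24%.
5. Remove the more-than-30-samples justification.
6. State that 6 of 36 does not control error when the SD of the change exceeds the baseline SD (5.0% per marker at correlation 0.4, 12% at 0.25), and treat the choice of yardstick as its own question.

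Cost: SAP wording, a short simulation and one more responder for a positive result. Power at the 35% target falls from 99.9% to 99.6%. No additional patients, samples or visits are needed.

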7.8 Alpha error correction through multiple analyses

(ICH E3; 9.7.1, 11.4.2.5. ICH E9; 2.2.5)

The type-I error for primary biomarker analysis is 10%. As we analyze the inhibition of three biomarkers as primary variable (cyclin D1, Ki67 and active caspase 3), the type I error was divided into 3,3% (<5%) for each analysis.

Prior to the completion of the study, an interim analysis with a cut-off dated 08-May-2018 will be performed in case the study was not completed up to that date. The results will be presented at the ASCO annual meeting 2018. In order to correct the alpha error associated with multiple primary analyses, it was considered that only statistically significant biomarker differences could be declared when the analysis showed p-values <3.3% in the interim and the final analyses for both analysis populations (full analysis set and per protocol set).

For secondary analyses (analysis of the difference and correlation between the levels of different biomarkers), multiple analyses were corrected through Benjamini-Hochberg's procedure "false Discovery rate (FDR)" of 10%. This procedure lists the analyses performed from lowest to highest p-value. A difference is considered statistically relevant in an analysis if the p-value obtained is equal or lower than the range assigned in that analysis, divided into the number of analyses and multiplying by 10%.

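### SAP 5.4 gives 95% power at a 35% response rate, but its 5-of-36 rule has 99.9% power at that rate and reaches 95% at about 23.6%

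*SAP*

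**What the plan says.** SAP 5.4 first defines response for a single patient: a biomarker reduction of at least 50% that also exceeds 1.6448 baseline standard deviations on the log scale, which is a one-sided 0.05 test. It then sets the study-level rule: "Significant inhibition of biomarker activity will be declared if 5 of 36 patients have significant inhibition at patient level". For that rule it claims that "there is a 95% power to detect a true 35% rate of significant inhibition with an overall alpha error below 10" per cent, with the type I error split into 3.3% for each of cyclin D1, Ki67 and active caspase 3. Both figures are attributed to the binomial distribution.

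Three other statements bear on the claim.

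- **Dropouts (5.4):** "We assume the loss of patients between recruitment and end of study". Those patients count as not showing inhibition. No dropout rate is given.
- **Basis of the sample size (5.4):** the number was fixed "for clinical and practical considerations, rather than statistical ones", and the power analysis is described as preliminary.
- **Conditions for success (7.8 and 7.6):** 7.8 asks for p-values below 3.3% "in the interim and the final analyses for both analysis populations (full analysis set and per protocol set"). 7.6 adds: "The analyses are only considered positive if the result is equivalent in all the analysis populations used".

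**The concern.** Power at a stated true rate depends only on the number of patients, the cut-off and that rate. SAP 5.4 gives all three and names the distribution, so the 95% can be checked directly. A cut-off of 5 in 36 is an observed rate of 13.9%. If the true rate is 35%, about 12.6 responders are expected (36 × 0.35), so a miss should be much rarer than 1 in 20.

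What is at stake is how the rule's sensitivity is described. SAP 3.1 says phase 0 studies help with the decision to continue or stop a drug. A reader of 5.4 would conclude that about 35% is the rate this rule detects with 95% power. In fact the rule does so for a rate more than 11 percentage points lower (35 − 23.6 = 11.4).

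**Working it through.** **Inputs, all from SAP 5.4**

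- Patients: n = 36 ("the sample size has been limited to 36 patients").
- Rule: success if the number of responders X is at least 5.
- True rate: 35%. Stated power: 95%.
- Null rate: not labelled. The patient-level test at the one-sided 0.05 level implies a nominal 5%.
- Stated type I error: 3.3% per biomarker, below 10% overall.
- Dropouts: counted as non-responders, so n stays at 36. No rate is given.

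**Formula**

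P(X ≥ 5) = 1 − Σ (k = 0 to 4) C(36, k) p^k (1 − p)^(36 − k)

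**Step 1. The type I error reproduces.** At p = 0.05 the terms for k = 0 to 4 are 0.1578, 0.2990, 0.2753, 0.1642 and 0.0713, which sum to 0.9676. So P(X ≥ 5) = 0.0324, or 3.24% per biomarker. Summed over three this is 3 × 0.03236 = 9.7%; if the biomarkers were independent it would be 1 − (1 − 0.03236)³ = 9.4%. Both stated bounds hold. Neighbouring cut-offs fit less well: at least 4 gives 10.4% per biomarker and at least 6 gives 0.8%.

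**Step 2. The power does not reproduce.** At p = 0.35 the terms for k = 0 to 4 sum to 0.00115, so P(X ≥ 5) = 0.99885, or 99.9%. The plan says 95%.

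**Step 3. Where the rule does have 95% power.** Solving P(X ≥ 5) = 0.95 gives p = 0.2365 (23.648%, or 23.6% to one decimal).

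| True rate | Power of at least 5 of 36 |
|---|---|
| 20% | 87.3% |
| 23.6% | 95% |
| 25% | 96.6% |
| 30% | 99.3% |
| 35% | 99.9% |

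**Step 4. Could another reading give 95% at 35%?**

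- More than 5 responders (at least 6): 99.6%.
- Other cut-offs: at least 7 gives 98.7%, at least 8 gives 96.7%, at least 9 gives 92.7%. None gives 95%.
- Normal approximation in place of the exact binomial: 99.6% to 99.8%.
- Success required for all three biomarkers, each with a true rate of 35%: at least 99.65%, from 1 − 3 × (1 − 0.99885).

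**Step 5. Could dropouts explain it?** With a proportion d lost and counted as non-responders, the effective rate is 0.35 × (1 − d). The values of d are assumed.

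| Loss d | Effective rate | Power |
|---|---|---|
| 10% | 31.5% | 99.6% |
| 20% | 28.0% | 98.6% |
| 30% | 24.5% | 96.1% |
| 32.4% | 23.7% | 95.0% |

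Reaching 95% takes d = 1 − 0.23648/0.35 = 32.4%, or about 12 of 36 patients.

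**The case against.** **The error is on the safe side.** The rule has more power at 35% than claimed, and the sentence would be true if it said at least 95%. The power analysis is called preliminary, and 36 was not derived from it. All of this stands, and it is why the point is minor. It does not make the sentence right: 5.4 does not say at least, and a power statement is read as identifying the effect the rule can detect.

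**An assumption may have been left out.** SAP 5.4 does expect losses, and a loss of about 32% would give 95%. That is possible, but no rate is stated, and at 10% or 20% loss power stays above 98%. An interim requirement is another candidate, but 5.4 does not mention one and no interim sample size is given.

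**Stronger readings that the documents do not support**

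- *That the null rate cannot be recovered, or the type I error cannot be checked.* A reader might infer this because 5.4 never labels a null rate. But the same section sets the patient-level test at the one-sided 0.05 level, and a 5% null reproduces the stated bounds (step 1). The gap is one of labelling.
- *That sections 7.6 and 7.8 cost a known, large amount of power.* Requiring success more than once does lower power, but the size cannot be worked out from the documents. SAP 7.8 sets a p-value threshold, not a fixed count of 5, so a smaller set could pass with fewer responders. The interim takes place only if the study is not complete by its cut-off of 08-May-2018. SAP 7.2 waives repeat analyses when populations differ by only 10% of patients.
- *That the sample size or the cut-off is wrong.* Nothing in the calculation requires either to change.

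**Conclusion.** The stated power is wrong as written. For at least 5 responders among 36, power at a true 35% rate is 99.9%, a gap of 4.9 percentage points from the stated 95%. The rate detected with 95% power is about 23.6%. No assumption stated in the documents closes the gap. These figures rest on a single final analysis of one biomarker, with all 36 patients counted and none lost.

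The type I error claim stands, given the nominal 5% null implied by the patient-level test. Because the mistake understates power, and neither the rule nor the sample size depends on it, this is a minor correction to the description of the rule.

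**What to change.** In SAP 5.4, replace the power sentence with:

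> With at least 5 of 36 responders, a 5% null rate, a single final analysis and all 36 patients counted, type I error is 3.2% per biomarker (9.7% over three) and power is 99.9% at a true rate of 35%, 95% at 23.6% and 87% at 20%. Dropouts counted as non-responders lower this (at 35%: 99.6% with 10% loss, 98.6% with 20%).

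If the 95% at 35% rests on a dropout or interim assumption, state that assumption and its size instead.

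Add one sentence: power is lower if the conditional interim analysis takes place, or if the full analysis and per-protocol sets differ enough for both to be analysed, because 7.8 then requires success in each.

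The cost is one paragraph in 5.4. The 5-of-36 rule and the sample size of 36 stay as they are.
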